1.5 Rationale for Use in Colorectal Cancer

The intended outcome of successfully and significantly mitigating regorafenib-induced HFSR is that patients will be able to stay on the regorafenib for a longer period to increase efficacy. The hypothesis underlying this trial is that the co-administration of perindopril with regorafenib will mitigate HFSR symptoms.

This may not be the case, and if the HFSR is more severe with the addition of perindopril than with regorafenib alone, the study will be discontinued.

As a secondary endpoint, hypertension will also be followed.

1.6 Clinical experience with Regorafenib

47% of regorafenib treated patients in the CORRECT trial experienced HFSR of all grades, while 17% experienced grade 3 HFSR. Results of the CONCUR Trial were similar. Although 74.3% of patients experienced any grade of HFSR, 16.2% experienced grade 3.

All efforts need to be made to find new therapeutic combinations to reduce HFSR, as it causes a significant decrease in a patient's quality-of-life.

Expected time on trial: In the CORRECT trial (regorafenib versus placebo) overall survival was 6.4 vs 5.0 months (HR=0.77, p=0.0052) and PFS was 1.9 vs 1.7 months (HR=0.49, p<0.000001). In the CONCUR trial, (regorafenib versus placebo) overall survival was 8.8 versus 6.3 months (HR=0.550, 95% CI 0.395-765, p=0.0002 (I sided). PFS was 3.2 versus 1.7 months (HR=0.311, 95% CI 0.222-0.435, p<0.0001 (1 sided)).

Based on CONCUR, expected time patients will stay on trial is four months.

2. Study objectives

This trial will measure the incidence and severity of HFSR and hypertension in patients receiving both perindopril and regorafenib.

The incidence of HFSR will be expressed as the number of patients out of study (N=34) who are experiencing HFSR of all grades. Severity will be evaluated using CTCAE v4.03 criteria.

The incidence of hypertension will be expressed as the number of patients on study (N=34) who are experiencing hypertension of all grades. Severity will be evaluated using CTCAE v4.03 criteria.

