For subjects who require a dose reduction for Grade 2 or 3 rash or hand-foot skin reaction (HFSR), the dose of study drug may be increased to the starting dose after one full cycle of therapy has been administered with the reduced dose without the appearance of rash or HFSR > Grade 1.

The following measurements should be considered for prevention and treatment of HFSR:

Control of calluses

Before initiating treatment with regorafenib:

- Check condition of hands and feet
- Suggest a manicure/pedicure, when indicated
- Recommend pumice stone use for callus or 'rough spot' removal.

During regorafenib treatment:

- Avoid pressure points
- Avoid items that rub, pinch, or create friction.

Use of creams

Apply non-urea based creams liberally.e.g.:

Keratolytic Creams: Use sparingly and only to affected (hyperkeratotic) areas

- Urea-based creams
- Salicylic acid 6%

Alpha Hydroxy Acids (AHA) based creams

- Approximately 5-8% provide gentle chemical exfoliation
- Apply liberally two times each day

Topical analgesics like lidocaine 2% to be considered for pain control

Topical corticosteroids like clobetasol 0.05% should be considered for subjects with Grade 2 or 3 hand-foot skin reaction. Avoid systemic steroids.

Cushions

Protect tender areas

- Use socks/gloves to cover moisturizing creams
- Wear well-padded footwear
- Use insole cushions or inserts (e.g., silicon, gel)
- Foot soaks with tepid water and Epsom salts

Phase II Study of Perindopril and Regorafenib in mCRC (PARICCA)

Table 5: Dose modification for Treatment-Emergent Hypertension			
Grade of Event (CTCAE version 4.03)	Definition	Anti-hypertensive therapy	Regorafenib dosing
Grade 1	Pre-hypertension (systolic BP 120-139 mmHg or diastolic BP 80-89 mmHg)	None	Continue regorafenib. Consider increased blood pressure monitoring.
Grade 2	Systolic BP 140-159 mmHg or diastolic BP 90-99 mmHg OR Symptomatic increase by > 20 mmHg (diastolic) if previously within normal limits	Treat with the aim to achieve diastolic BP ≤ 90 mmHg -If BP previously within normal limits, start anti-hypertensive monotherapy -If subject already on anti-hypertensive medication, titrate up the dose	Continue regorafenib. If symptomatic, hold regorafenib until symptoms resolve AND diastolic BP ≤ 90 mmHg ^a . When regorafenib is restarted, continue at the same dose level.

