7.5.1 Adverse events

7.5.1.1 Definitions

Definition of adverse event (AE)

In a clinical study, an AE is any untoward medical occurrence (i.e. any unfavorable and unintended sign [including abnormal laboratory findings], symptom or disease) in a patient or clinical investigation subject after providing written informed consent for participation in the study. Therefore, an AE may or may not be temporally or causally associated with the use of a medicinal (investigational) product.

Surgeries and/or procedures are not Adverse Events – they are therapeutic measures for conditions that require such intervention. However, the condition requiring surgery may be an Adverse Event. Therefore, if surgical procedure is reported, the basic condition leading to surgery is entered as event respectively.

Disease progression in itself should not be reported as an AE. However, if disease progression results in events that fit AE definition, these should be reported as such.

In the following differentiation between medical history and AEs, the term “condition” may include abnormal physical examination findings, symptoms, diseases, laboratory, or ECG.

- Conditions that started before signing of informed consent and for which no symptoms or treatment are present until signing of informed consent are recorded as medical history (e.g. seasonal allergy without acute complaints).

Phase II Study of Perindopril and Regorafenib in mCRC (PARICCA)

- Conditions that started before signing of informed consent and for which symptoms or treatment are present after signing of informed consent, at *unchanged intensity*, are recorded as medical history (e.g. allergic pollinosis).
- Conditions that started or deteriorated after signing of informed consent will be documented as adverse events.

In this study, investigators should also report signs and symptoms that are associated with progressive disease or the worsening of the existing cancer, and avoid using the AE term progressive disease.

Definition of serious adverse event (SAE)

An SAE is classified as any untoward medical occurrence that, at any dose, meets any of the following criteria (a – f):

a. Results in death

b. Is life-threatening

The term ‘life-threatening’ in the definition refers to an event in which the patient was at risk of death at the time of the event, it does not refer to an event which hypothetically might have caused death if it were more severe.

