8.4 Secondary Objectives

The secondary objectives are to evaluate the time to development of worst grade 3 HFSR toxicity, proportion of all grades of hypertension, proportion of all grade toxicities and progression-free survival. All toxicities will be evaluated using CTCAE v4.03.

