8.4.1 Time to worst grade 3 HFSR toxicity

Time to worst grade 3 HFSR toxicity is defined as the time (days) from start date of study drug to date of first documented grade 3 HFSR toxicity and will be calculated only for patients who had a HFSR toxicity grade 3.

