8.5 Safety

Safety variables are as follows: adverse events, the number of laboratory values that fall outside of pre-determined ranges (hematology, clinical chemistry and clinical urinalysis), changes in vital signs (blood pressure, heart rate, respiratory rate, temperature) and electrocardiogram (ECG).

Phase II Study of Perindopril and Regorafenib in mCRC (PARICCA)

All adverse events whether considered drug-related or not, will be reported with start/stop dates, action taken, whether treatment was discontinued, any corrective measures taken, and outcome. For all events, the relationship to treatment and the severity of the event will be determined by the Investigator, using the terms and definitions given in Section 5.1.

A Treatment-emergent adverse event is defined as any event arising or worsening after the start of study drug administration until 30 days after the last study medication

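### Does the all-grade hypertension count need its own onset rule, given that grade 1 already starts at 120/80 mmHg?

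*Combined protocol and SAP*

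**What the plan says.** Hypertension is a secondary endpoint. Section 2 states the count: "The incidence of hypertension will be expressed as the number of patients on study (N=34) who are experiencing hypertension of all grades". The Synopsis (Methodology) and 7.5.1.2 repeat it, 2.2 adds an assessment schedule, and 8.4 lists "proportion of all grades of hypertension" among the secondary objectives.

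The grades are CTCAE v4.03. Table 5 in 6.4.2, titled "Table 5: Dose modification for Treatment-Emergent Hypertension", gives grade 1 as "Pre-hypertension (systolic BP 120-139 mmHg or diastolic BP 80-89 mmHg". Sections 5.1.2 and the Synopsis exclude pressure above 150 systolic or 90 diastolic despite optimal management, pressure below 90/60, and prior ACE inhibitor or ARB treatment. A patient can therefore enter at grade 1 or in the lower part of grade 2.

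Two onset rules appear elsewhere:

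- Section 7.5.1.1 is anchored at consent: "Conditions that started or deteriorated after signing of informed consent will be documented as adverse events". Its preceding bullet assigns conditions that continue from before consent at the same intensity to medical history.
- Section 8.5 is anchored at first dose and defines a treatment-emergent event as "any event arising or worsening after the start of study drug administration until 30 days after the last study medication".

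Section 8.5 also lists "changes in vital signs (blood pressure, heart rate, respiratory rate, temperature" among the safety variables. Section 8.1 limits secondary safety variables to descriptive statistics and exploratory graphs.

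**The concern.** Grade 1 is so low that many adults reach it without any drug. If the count means any reading at grade 1 or above while on study, it mostly describes the blood pressure patients brought with them. A patient at 125 mmHg before and throughout treatment would be an event.

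The omission looks pointed because two other secondary endpoints do have definitions. Section 8.4.1 begins: "Time to worst grade 3 HFSR toxicity is defined as the time (days) from start date of study drug". Section 8.4.2 starts progression-free survival at the same date. Hypertension has no such subsection.

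At stake is how the rate is read. Section 1.1 expects perindopril to reduce hypertension, and 1.2 gives any-grade rates of 28% (CORRECT) and 25% (CONCUR). If the counting rule were picked after the data were seen, the reported rate could land near those figures or far above them.

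**Working it through.** **1. The plan's own figure.** The denominator 34 comes from the HFSR calculation in 8.7, with p0 = 0.47, p1 = 0.24, two-sided 5% and 80% power:

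n = [1.960 × √(0.47 × 0.53) + 0.8416 × √(0.24 × 0.76)]² / (0.47 − 0.24)² = (0.978 + 0.359)² / 0.0529 = 33.8, rounded up to 34.

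It reproduces. Nothing in it depends on hypertension, for which the plan sets no target or power.

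**2. The unchanged patient under each rule.** Take 125 mmHg before consent, at first dose and throughout.

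| Reading | Counted? |
|---|---|
| Section 2 sentence alone | Yes |
| 7.5.1.1 (started or deteriorated after consent) | No, medical history |
| 8.5 (arose or worsened after first dose) | No |

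The two rules disagree only for a grade that appears between consent and first dose and then persists: an AE under 7.5.1.1, not treatment-emergent under 8.5. Each such patient moves the rate by 1/34 = 2.9 points. The documents do not say how many there would be.

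**3. What the literal reading would add.** Let e be the treatment-emergent proportion and b the share entering at grade 1 or above. Assuming independence, literal proportion = b + (1 − b)e. With e = 0.28 (CORRECT's rate, for illustration; 9.5 of 34) and b assumed:

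| b | Literal proportion | Of 34 |
|---|---|---|
| 0.10 | 0.10 + 0.90 × 0.28 = 0.352 | 12.0 |
| 0.20 | 0.20 + 0.80 × 0.28 = 0.424 | 14.4 |
| 0.40 | 0.40 + 0.60 × 0.28 = 0.568 | 19.3 |
| 0.60 | 0.60 + 0.40 × 0.28 = 0.712 | 24.2 |

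**4. Simulation on assumed pressures.** Assumptions: mean entry systolic 115 to 130 mmHg, SD 12 between and 8 within patients, entry reading 90 to 150, systolic criterion only, seven on-treatment readings (Table 7, cycle 1 day 7 to cycle 3 day 1), no drug effect.

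| Rule | Mean 115 | Mean 130 |
|---|---|---|
| Any reading at 120 or above (literal) | 0.696 | 0.944 |
| Any reading above the pre-dose grade | 0.433 | 0.536 |
| Rise at two consecutive visits | 0.172 | 0.259 |

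The fair comparator is the middle row, which is closest to 8.5: 0.696 − 0.433 = 0.263 and 0.944 − 0.536 = 0.408, or 26 to 41 points. Against the bottom row the gap is 52 to 69 points, but a two-visit rule appears nowhere in the plan.

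The model also grades every raw reading for every patient. In the plan the investigator assesses adverse events (7.5.1.2), and a physician confirms diary readings before they enter the case report form (7.1.2.2). Cycle 3 day 1 falls 56 days, about 1.8 months, after first dose, while median progression-free survival in 1.6 is 1.9 and 3.2 months. Many patients may not supply all seven readings.

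**5. What a settled rule could support.** Suppose the true rate were half of CORRECT's: 0.14 × 34 = 4.8, say 5 events. The exact 95% interval for 5/34 is 5.0% to 31.1%, which still contains 28% and 25%. For 10/34 it is 15% to 47%. CORRECT also graded with CTCAE v3.0 (14.2), so the comparison is weak whichever rule is used.

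**The case for a change.** The best case for a change is that the existing rules are not attached to this endpoint. Section 2.2 lists hypertension apart from general toxicity and on its own schedule. No endpoint sentence cites 7.5.1.1 or 8.5, the two rules have different anchors, and neither says that worsening means a rise in grade. Repeat readings are requested at screening and in self-measurement, without saying which value is graded. Nor does Table 5 say whether protocol perindopril counts toward its grade 3 clause on more than one drug. A sentence in 8.4 would cost almost nothing.

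All of that is accurate, and the missing link stands as a matter of drafting. It does not leave the analyst at a loss. The endpoint is worded as an incidence, its sentence is repeated in the adverse-event classification section directly after the 7.5.1.1 definitions, and 8.4 places it among toxicities. Section 8.5 holds the only onset definition in the statistical section, and its anchor matches the first-dose start used in 8.4.1 and 8.4.2. Worst grade above the last pre-dose grade is the ordinary way to apply it, and pre-dose pressure is already scheduled. Baseline summaries (8.1) and changes in blood pressure (8.5) show the reader how much was there at entry.

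The larger additions are trade-offs. A confirmation rule loses brief true rises. Same-visit clinic repeats on treatment are not clearly required, and from cycle 3 Table 7 has one reading per cycle, so confirmation could come four weeks later. A separate grade 2-or-above rate, or grade 3 split by trigger, is a matter of taste here.

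Separately, 7.1 mentions a blood pressure reading at the follow-up visit, whereas Table 7 and 7.1.2.4 show none there and 7.1.2.4 allows a telephone contact. That is a clerical mismatch and does not affect the onset question.

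**Conclusion.** No change to the plan is needed. The literal reading that creates the problem requires setting aside both onset rules, and either one excludes the patient whose pre-consent grade never changes. The remainder is a missing cross-reference that an analyst would fill sensibly with the 8.5 definition, for a secondary, descriptive endpoint.

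The documents do not allow the size of any effect on the rate to be derived. The 26 to 41 points, and the 12.0 to 24.2 of 34 against 9.5, rest on assumed entry pressures or an assumed share entering at grade 1 or above, and describe an analysis that the plan's own adverse-event rules do not support. The real ambiguity, between consent and first dose as anchor, is worth 2.9 points per affected patient, and their number is unknown. The HFSR test, N=34 and its 80% power do not change. With 34 patients in one arm and a different CTCAE version from CORRECT, a firmer definition would not make a claim of reduced hypertension supportable.

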2.1 Primary outcome

Incidence of all grade toxicities for HFSR will be evaluated.

Patients will be seen by physician every week for the first six weeks, then every two weeks after (see attached study schedule, APPENDIX A).

Subjects are to be evaluated for symptoms and AEs in a visit **30 days (+7 days)** after permanently stopping study treatment. After the last contact of the Safety Follow-Up Visit (or after the EOT visit if the Safety Follow-Up Visit is not available), subjects will be off study.

2.2 Secondary outcomes

- Hypertension: All grades of hypertension will be evaluated using CTCAE v4.03, weekly for the first six weeks while they are on the study drug, then every second week and during the 30-day follow up period (Post therapy)(see attached study schedule, APPENDIX A).

Phase II Study of Perindopril and Regorafenib in mCRC (PARICCA)

- Toxicity: all grades of AE including HFSR will be evaluated using CTCAE v4.03, at baseline and at D1 of each cycle while they are on the study drug and during the 30-day follow up period (Post therapy).
- Time course to development of worst grade (grade 3) HFSR.
- PFS will be evaluated based on RECIST v1.1 criteria, 20% progression or any new lesion.

3. Investigators and other study participants

Study sponsors and PIs:

[name], [name]
BC Cancer Agency – Vancouver Cancer Centre
[name]
[name]

3.1 Data Monitoring Committee

Not applicable – ISS.

3.2 Clinical Trials Nurse Coordinator (CTNC)

Reporting to the Clinical Trials Unit Manager (VCC), Operations Cancer Care Leader (CCSI, VICC and FVCC), or designate, the Clinical Trials Nurse Coordinator (CTNC) receives direction from Principal Investigators or designates, and is professionally accountable to the Professional Practice Leader in Nursing.

The CTNC participates in the coordination of clinical trials from the protocol review and approval stage through to activation, trial closure and follow-up.

The CTNC has principal responsibility for the coordination of the treatment programs, nursing care, monitoring, clinical assessment, and education of patients participating in the assigned clinical trials. The CTNC has formal responsibility for advising or teaching nursing staff in clinic and treatment areas on specialized theory and practice related to clinical trials.

3.3 Clinical Trials Data Coordinator (CTDC)

The Clinical Trials Data Coordinator (CTDC) receives direction from Principal Investigators or designates, and receives general supervision in matters related to Patient Information Management from the Chief Paramedical, PIM.

The CTDC has principal responsibility for clinical trials data management, including designing data capture tools, capturing and recording clinical trials data, monitoring and promoting the quality and integrity of data, and preparing summary reports. Data management is performed in accordance with trial protocol, procedures, guidelines and professional standards of practice.

Phase II Study of Perindopril and Regorafenib in mCRC (PARICCA)

3.4.1 Biostatistician

Reporting directly to the Principal Investigator, the biostatistician will provide statistical support as well as some database management support. Statistical support includes: protocol design and development and REB application, support in design of data collection forms, statistical analysis plan, statistical analysis and provision of the final statistical analysis report. Data Management Support includes database design and development, data dictionary, data review, coding and cleaning ready for analysis.

3.5 Location of laboratory and imaging facilities

[figure not shown]
The laboratory and imaging facilities for this study are both located on the 3rd floor of the BC Cancer Agency at [name].

4. Study design

Phase II, open-label, single-arm trial of patients with refractory mCRC treated with regorafenib (160 mg/day) and perindopril (4 mg/day).

This study will be conducted at the BC Cancer Agency (Vancouver Centre) only.

PARICCA trial design

Primary endpoint: Incidence of all grade toxicities for HFSR

Secondary endpoints: Incidence of (all grade) hypertension & toxicity; Severity of HFSR; Time course to development of worst grade (stage3) HFSR; Progression Free Survival.

Treat until progression, unacceptable toxicity, or withdrawal

During the study period, patients will undergo evaluations for safety and drug accountability every cycle. Drug safety will be monitored and evaluated continuously throughout the study, including a 30-day follow up period. Patients will continue on treatment until one of the following occurs (main criteria):

- Progressive Disease as defined by Response Evaluation Criteria in Solid Tumors (RECIST) criteria, version 1.1, or clinical progression
- Death
- Unacceptable toxicity
- Patient withdraws consent
- Treating physician determines discontinuation of treatment is in the patient's best interest
- Substantial non-compliance with the protocol

For the full list of criteria refer to section 5.2.1.

If in the Investigator's opinion, treatment with regorafenib is providing clinical benefit to a patient experiencing disease progression, the patient may continue treatment.

Justification of the design

47% of regorafenib treated patients in the CORRECT trial experienced HFSR of all grades, while 17% of regorafenib patients experienced grade 3 HFSR. All efforts need to be made to find new therapeutic combinations to reduce HFSR, as it causes a significant decrease in a patient's quality-of-life.

Although we are assuming that the co-administration of perindopril with regorafenib will mitigate HFSR symptoms, this may not be the case. If the HFSR is more severe with the addition of perindopril than with regorafenib alone, the study will be discontinued.

The choice of dosage and schedule to be used in this trial comes from data accumulated in previous phase III trials with regorafenib (CORRECT, CONCUR). The choice of dosage and schedule for perindopril is from the Coversyl monograph.

End of study

The study will conclude with the last visit of the last patient.

5. Study population

